4.2.11. INJECTION SITE REACTION ASSESSMENT

Local injection sites reactions will be assessed on Day 0 post injection, Day 14, Day 21, Day 30 and Day 60 using the grading defined by the National Cancer Institute's Common Terminology for Adverse Events v3.0. The grading categories are as follows and will be recorded on the CRF as described in

Table 3. Injection Reaction Assessment

Table 3.

ADVERSE EVENT	GRADE 1	GRADE 2	GRADE 3	GRADE 4	GRADE 5
Injection site reaction	Pain, itching, erythema	Pain or swelling, with inflammation or phlebitis	Ulceration or necrosis that is severe; operative intervention indicated		
Ulceration		Superficial ulceration < 2 cm size; local wound care; medical intervention indicated	Ulceration ≥2 cm size; operative debridement, primary closure or other invasive intervention indicated (e.g. hyperbaric oxygen)	Life- threatening consequences; major invasive intervention indicated (e.g., complete resection, tissue reconstruction, flap, or grafting	Death
Allergic reaction / hypersensitivity	Transient flushing or rash; drug fever < 38°C (<100.4°F)	Rash; flushing ; urticaria; dyspnea; drug fever ≥38°C (≥100.4°F)	Symptomatic bronchospasm, with or without urticaria; parenteral medications(s) indicated; allergy- related edema/ angioedema; hypotension	Anaphylaxis	Death

5. **EVALUATION OF ADVERSE EVENTS**

5.1. **DEFINITIONS**

An Adverse Event (AE) is the development of an untoward medical occurrence or the deterioration of a pre-existing medical condition following or during exposure to an investigational product, whether or not considered causally related to the product.

An untoward medical condition can be symptoms (e.g., nausea, chest pain), signs (e.g., tachycardia, enlarged liver) or clinically significant abnormal results of an investigation (e.g., laboratory findings, electrocardiogram).

A serious adverse event (SAE) is any untoward medical occurrence which:

- Results in death;
- Is life-threatening;
- Requires inpatient hospitalization or prolongation of hospitalization which is not specifically required by the protocol or is elective;
- Results in permanent impairment of a body function or permanent damage to a body structure; or
- Requires medical or surgical intervention to preclude permanent impairment of a body function or permanent damage to a body structure.

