Additionally, important medical events that may not result in death, be lifethreatening or require hospitalization may be considered SAEs when they jeopardize the patient or require medical or surgical intervention to prevent one of the serious outcomes listed above. Examples of such medical events include: allergic bronchospasm requiring intensive treatment in an emergency room or at home, blood dyscrasias or convulsions that do not result in inpatient hospitalization or the development of drug dependency or drug abuse. Medical and scientific judgment must be exercised when classifying events as serious.

Life-threatening means that the patient is, in the view of the investigator, at immediate risk of death from the AE as it occurred. It does not include an AE which, had it occurred in a more serious form, might have caused death.

Persistent or significant disability/incapacity means that the event resulted in permanent or significant and substantial disruption of the patients' ability to carry out normal life functions.

An unexpected AE is an AE, the nature or severity of which is not consistent with the applicable product information (e.g. Investigator Brochure for an unapproved product). Expected means that the event has been previously observed with the test article and is identified and/or described in the applicable product information. It does not mean that the event is expected with the underlying disease(s) or concomitant medications. It is expected that certain disease states will have reoccurring adverse events some of which may be considered expected over time.

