5.4.2. SPONSOR'S RESPONSIBILITY

All AEs and SAEs will be reported on and annual basis to FDA in accordance with the IND regulation (21 CFR Part 312). All serious unexpected AEs will be reported to FDA as an IND Safety Report with 15 calendar days of the event (21 CFR §312.32). Any unexpected fatal or life-threatening AEs will be reported to the Agency within 7 calendar days.

ViroMed will notify all participating investigators of any new safety information that alters the current risk-benefit assessment of the study medication or that would be sufficient to consider changes in VM202 administration or in the overall conduct of the trial.

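### Section 5.1 leaves significant but non-permanent disability outside the listed SAE criteria, and gives two incompatible statements of what counts as expected for FDA reporting

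*Combined protocol and SAP*

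**What the plan says.** Section 5.1 lists five criteria for a serious adverse event: death, threat to life, hospitalisation, and two that turn on permanence. The fourth is "Results in permanent impairment of a body function or permanent damage to a body structure; or" and the fifth is "Requires medical or surgical intervention to preclude permanent impairment of a body function or permanent damage to a body structure".

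A further paragraph brings in important medical events, which "may be considered SAEs when they jeopardize the patient or require medical or surgical intervention to prevent one of the serious outcomes listed above", and asks for medical and scientific judgment. The section then explains a term that appears in none of the five criteria: "Persistent or significant disability/incapacity means that the event resulted in permanent or significant and substantial disruption" of normal life functions.

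On expectedness, Section 5.1 refers to the applicable product information, such as the Investigator Brochure, and adds: "It does not mean that the event is expected with the underlying disease(s) or concomitant medications". The sentence that follows is: "It is expected that certain disease states will have reoccurring adverse events some of which may be considered expected over time".

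These definitions are used in three places:
- Section 5.4.1: the investigator reports any SAE to the sponsor and CRO within 48 hours, whether or not it is related.
- Section 5.4.2: "All serious unexpected AEs will be reported to FDA as an IND Safety Report with 15 calendar days of the event"; unexpected fatal or life-threatening events go within 7 days; all AEs and SAEs are reported annually.
- Section 6.2.1: AEs and SAEs are summarised descriptively.

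**The concern.** A definition placed among the SAE definitions but attached to no criterion suggests that a criterion was left out. The threshold in the definition (permanent, or else significant and substantial) is lower than the threshold in the list (permanent only). A disabling but reversible event can meet the first and fail the second.

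The two expectedness sentences pull in opposite directions. Under the first, an event is not expected merely because diabetes or neuropathy can cause it. Under the second, some recurring events of the disease may become expected.

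Safety and tolerability are the primary endpoint, and SAEs are a named summary category. The trial is multicenter and open label, with dose cohorts only, so there is no untreated arm to show the background rate of disease-related events. Section 1.1 lists muscle weakness, poor coordination, foot ulceration and infection among the features or consequences of the disease, so harm in the injected leg could resemble it. What is at stake is whether an event gets the right label and a prompt report.

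**Working it through.** The plan gives no figure to reproduce here. The check takes two illustrative events through the rules.

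**Event A:** foot weakness that substantially disrupts normal life for some months and then resolves, with no hospitalisation and no intervention to prevent permanent damage.

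1. Against the five listed criteria: not fatal, not life-threatening, not hospitalised, not permanent, and no intervention to preclude permanence. It meets 0 of 5.
2. Against the disability definition: it meets the second alternative, significant and substantial disruption. No criterion uses that definition, so this has no effect.
3. Against the important-medical-event clause: the intervention limb refers back to the listed outcomes and does not apply. The limb on jeopardising the patient remains. It is permissive, so two investigators could reasonably differ.

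**Event B:** a hospitalised foot infection of a kind typical of the disease, not described in the product information.

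1. It is serious through hospitalisation. Expectedness is not part of the SAE definition.
2. Under the first expectedness sentence it is unexpected. Under the second it may be treated as expected.

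| Output | Trigger | Event A | Event B |
|---|---|---|---|
| AE form and AE summary (5.2, 6.2.1) | any AE | included | included |
| Annual FDA report (5.4.2) | any AE or SAE | included | included |
| SAE summary (6.2.1) | serious | only through the clause | included |
| 48-hour report (5.4.1) | serious | only through the clause | included |
| 15-day FDA report (5.4.2) | serious and unexpected | only through the clause, and if unexpected | depends on the sentence followed |
| 7-day FDA report (5.4.2) | unexpected, and fatal or life-threatening | not applicable | depends on the sentence followed, if the event were fatal or life-threatening |

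The seriousness gap thus reaches three outputs: the SAE summary, the 48-hour report and the 15-day report. The expectedness conflict reaches two: the 15-day and 7-day reports.

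For scale, one reclassified patient changes the percentage with an SAE by:
- 1/4 = 25 points in a planned cohort
- 1/6 = 16.7 points in an expanded cohort
- 1/12 = 8.3 points in the planned total
- 1/14 = 7.1 points in the maximum total

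This is true of any single event in groups this small. It shows how coarse the summary is and says nothing about how often reclassification would occur.

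**The case against.** The strongest reply is that little is lost. Section 5.2 records every AE whatever its severity, with duration, seriousness and outcome, and follows it to resolution or stability. Section 6.2.1 summarises all AEs, and the synopsis adds a description by severity and relationship. Under Section 5.2.2, an event that significantly limits routine activities despite symptomatic therapy is severe, so Event A could well be tabulated as a severe AE. The important-medical-event clause lets a careful investigator call it serious. Permanence may be unknown at 48 hours, but follow-up reports allow later correction. All of this stands, and it narrows the point. It does not supply a criterion that makes Event A serious as a rule.

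On expectedness, the phrase about time leaves some room for interpretation, and the decision appears to lie with the sponsor: the AE form items in Section 5.2 include no expectedness field, and FDA reporting is the sponsor's task. The documents therefore do not show that sites would disagree on expectedness. The two sentences still point the sponsor in different directions.

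Three stronger readings are tempting and are not supported:
- *Disease-typical events drop out of the SAE count.* They do not. Neither the SAE summary nor the 48-hour report has an expectedness condition.
- *Section 5.1 flatly contradicts itself on seriousness.* It is a mismatch: a defined term goes unused and its threshold is broader than the listed one.
- *Dose escalation is compromised.* Under Section 3.2 the DSMB reviews adverse events and DLTs. DLTs are described as SAEs, but they are three named events (anaphylaxis, fever, injection-site necrosis), none framed by disability or expectedness.

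**Conclusion.** Both defects are in the current text and feed operative rules. Followed as written, the seriousness list can leave a significant, non-permanent disability out of the SAE summary, the 48-hour report and the 15-day report unless the judgment clause is used. The expectedness sentences can cost a disease-typical event its 15-day or 7-day FDA report and nothing else.

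The conclusion rests on a plain reading of Section 5.1 and assumes that the important-medical-event clause is discretionary, as its wording indicates. It assumes no event rate: the available text gives none for lasting nerve or muscle impairment, so a reader should not infer that such events are likely or that harm will be lost from the data. Sample size is unaffected, no hypothesis is tested, and the DLT and escalation rules do not change. Severity is therefore moderate: worth correcting because it concerns prompt reporting in a safety study, but not a condition for the trial to proceed.

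**What to change.** Make two edits in Section 5.1:

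1. In the fourth seriousness bullet, add persistent or significant disability/incapacity (as defined below) as an alternative alongside the existing permanent impairment and damage wording. The definition already in the section then has a use.
2. Delete the sentence on recurring events of disease states, so that expectedness is judged only against the product information, as the preceding sentences say.

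Bring the SAE form into line with the revised list. The cost is two sentences and a form check. The downside is that slightly more events will be classed as serious or as unexpected, with the extra reports that follow.

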5.2. ASSESSMENT OF AES

All AEs, regardless of severity, occurring following the first study drug administration and the 12 month follow-up visit of the study by a patient must be recorded on the AE form provided with the CRF. This will include the following information:

- Description of the AE
- Date of onset
- Duration
- Frequency
- Severity
- Seriousness (yes/no)
- Treatment
- Outcome
- Relationship to study medication, injection procedure and/or underlying disease

All AEs and SAEs must be followed until resolution, or the condition stabilizes. The Investigator is responsible to ensure that follow-up includes any supplemental investigations as may be indicated to elucidate as completely as possible the nature and/or causality of the AE or SAE. This may include additional laboratory tests or investigations, histopathological examinations, or consultation with other health care professionals. ViroMed or its designee may request that the Investigator perform or arrange for the conduct of supplemental measurements and/or evaluations.

5.2.1. AE CAUSALITY

The study investigator will determine whether an AE is related or unrelated to study medication, the procedure (intramuscular injection) and / or the underlying disease using the following criteria:

Not related: An adverse event that is not related to the use of the test article or administration procedure.

Possibly related: An adverse event that might be due to the use of the test article or administration procedure. An alternative explanation, e.g., concomitant study product(s), concomitant disease(s), is inconclusive. The relationship in time is reasonable; therefore, a causal relationship cannot be excluded.

Probably related: An adverse event that might be due to the use of the test article or administration procedure. The relationship in time is suggestive. An alternative explanation is less likely, e.g., concomitant drug(s), concomitant disease(s).

Definitely related: An AE that is due to the use of the test article or administration procedure. The event cannot be reasonably explained by an alternative explanation – e.g., concomitant drug(s), concomitant disease(s).

5.2.2. AE INTENSITY

The intensity of the AE/SAE will be defined by the following criteria:

Mild: The AE is noticeable to the patient but does not interfere with

routine activity.

Moderate: The AE is discomforting and interferes with routine activity. Severe: The AE significantly limits the patient's ability to perform

routine activities despite symptomatic therapy.

5.3. REPORTING/RECORDING OF AES

Throughout the course of the study, all efforts will be made by the investigator to remain alert to possible AEs. The first concern will be the safety of the patient, and for providing appropriate medical intervention. The period of observation for collection of AEs starts during the first intramuscular injection procedure (Day 0) until the 12 month follow-up visit. Any AE should be recorded on the appropriate CRF page(s).

5.4. REPORTING / RECORDING OF SAES

5.4.1. INVESTIGATOR'S RESPONSIBILITY

SAES will be recorded following the first study drug administration and the 12 month follow-up visit. Any serious adverse event that occurs during this investigation, whether or not related to the study medication, must be reported immediately (within 48 hours) to the study sponsor and MedTech Consultants, Inc., the designated CRO.

Each SAE must be followed with appropriate medical management until resolved or assessed as chronic or stable regardless of whether or not, in the opinion of the Investigator, the event is thought to be related to the study medication.

The Investigator will be required to provide complete information concerning each SAE to the CRO and Sponsor within 5 calendar days of the event. This information must be recorded in the patient's medical record and then transcribed onto the SAE Form. The completed SAE Form (including the Investigator's opinion of the relationship of the SAE to the study medication), copies of related results/reports, consultant report(s), and other relevant information will be faxed and mailed to the CRO.

In the event of an SAE leading to hospitalization, every effort will be made by the investigational site to obtain medical records, including a hospital discharge summary. In the event of a fatal AE, documentation of any available postmortem findings, including autopsy, will be provided to ViroMed or their designee. In any

event, the Investigator will provide a narrative summary of circumstances, events related to the death, and cause of death, if known. Any follow-up information obtained must be recorded on an SAE follow-up report form.

The Investigator must comply with the applicable local regulatory requirements related to the reporting of SAEs to regulatory authorities and the Institutional Review Board (IRB), Institutional Biosafety Committee (IBC). Upon receipt from ViroMed of an initial or follow-up IND Safety Report or other safety information, the Investigator must promptly notify his or her IRB, IBC.

5.4.2. SPONSOR'S RESPONSIBILITY

All AEs and SAEs will be reported on and annual basis to FDA in accordance with the IND regulation (21 CFR Part 312). All serious unexpected AEs will be reported to FDA as an IND Safety Report with 15 calendar days of the event (21 CFR §312.32). Any unexpected fatal or life-threatening AEs will be reported to the Agency within 7 calendar days.

ViroMed will notify all participating investigators of any new safety information that alters the current risk-benefit assessment of the study medication or that would be sufficient to consider changes in VM202 administration or in the overall conduct of the trial.

6. STATISTICAL METHODS

The primary goal of this study is to determine the maximum tolerated dose that ensures patient safety. Sample size estimations were not based on formal statistical hypotheses testing due to the exploratory nature of this Phase I/II study. Hypothesis testing will not be performed on any endpoint.

6.1. **PATIENT CATEGORIZATION**

Screen Failure - Any patient who was consented and entered into the screening process appropriately, but subsequently did not meet the entry criteria in order to be treated. Patients who fail screening will not be followed for safety or efficacy assessment, and no other study procedures will be performed.

Evaluable Patient - Any patient who received the study drug.

Lost to follow-up - A patient deemed to be lost to follow-up is any patient who received treatment, but who does not complete scheduled study visits. This includes those patients who withdraw consent and refuse further study participation and all attempts to contact the patient are deemed unsuccessful.

6.2. STUDY ENDPOINTS

The primary study endpoint is to evaluate safety and tolerability of intramuscular injection in the calf of VM202 in patients with painful DPN. Secondary endpoints include the assessment of the potential of VM202 to reduce the pain associated with DPN.

6.2.1. SAFETY

Any patient who receives VM202 will be included in the safety analysis population. Adverse events, serious adverse events, and adverse events leading to treatment discontinuation will be summarized using descriptive statistics. Categorical variables will be summarized by the number and percentage of patients in each category. Continuous variables will be summarized using n, mean, SD, median, minimum, and maximum values. No statistical testing will be performed.

6.2.2. **PHARMACODYNAMICS**

HGF serum levels will be determined immediately pre-treatment on Day 0, immediately pre-treatment on Day 14, Day 30, and Day 60. Copies of VM202 in whole blood will be determined at Day 0 (pre-injection, and 2 hours post injection), at Day 14 (pre-injection, and 2 hours post injection), Day 21, Day 30, Day 60 and Day 90.

6.2.3. EFFICACY

This is a phase I /II study, not powered to detect differences in efficacy measures. However, descriptive statistics of clinically meaningful endpoints will be tabulated. Pain as measured by the VAS pain scale, the SF-MPQ and the BPI-DPN will be tracked and presented. The status of preexisting ulcers will also be reported.

7. ACCESS TO STUDY DOCUMENTS AND STUDY MONITORING

ViroMed will designate a CRO to monitor the progress of this study. The clinical monitor, as a representative of ViroMed, has the obligation to follow this study closely. In addition to conducting a site visit prior to initiation of enrollment, the clinical monitor will visit the study facilities regularly, and utilize telephone and written communications on an ongoing basis to maintain current knowledge of the study.

During periodic visits to the study site, the monitor will review the source documents used in the preparation of the CRFs to verify the accuracy and completeness of the information contained in those reports in preparation for retrieval. All source documents must be dated and signed by the person who performed the assessment or procedure, and must contain all information required by the CRF. All data generated during this study and the source documents from which they originated are patient to inspection by ViroMed or its representative, the FDA and other regulatory agencies.

Upon completion of the study, the clinical monitor will conduct a final visit (close-out) to the site. The objectives of this visit are to ascertain that all regulatory records and reports are complete, verify that study drug and other supplies have been accounted for and ensure that the investigator is aware of his/her responsibilities post-study.

8. **QUALITY CONTROL AND ASSURANCE**

ViroMed employees and/or their contracted representatives utilize Standard Operating Procedures (SOP) designed to ensure that research procedures and documentation are consistently conducted/prepared to the highest quality standards. These SOPs also require compliance with Health Authority regulations and Good Clinical Practice guidance.

A Quality Assurance audit may be conducted by ViroMed or its designee at any time during or after completion of a study. The Investigator will be given adequate notice if he/she is selected for an audit. The audit will include, but is not limited to, a review of all informed consent forms, a review of CRFs, associated source documents and medical records, a review of regulatory documentation, an assessment of study conduct and protocol compliance, and a review of the investigational drug accountability. At the conclusion of an audit, the auditor will conduct a brief meeting with the Investigator to review the findings of the audit.

